#### **TABLE OF TABLES**

#### **TABLE OF FIGURES**

This Statistical Analysis Plan (SAP) is intended to act as an outline for the statistical interpretation of the data resulting from the Phase 2B Investigational New Drug (IND) trial, titled: "A Phase 2B, Prospective, Double-Blinded, Randomized Controlled Trial of the Micronized dHACM Injection as Compared to Saline Placebo Injection in the Treatment of Osteoarthritis of the Knee." Specific questions regarding this trial's design and/or implementation may be addressed by the study protocol (AIOA001 Protocol V2).

This study consists of two phases – Main Phase and Open-Label Extension Phase (Extension Phase). The Main Phase of the study includes subjects during the observation period where they received the randomized treatment only. The Extension Phase of the study includes the subjects who elected to receive an open-label injection of micronized dHACM injection at either of the 180-day, 270-day or 365-day visits, during the 180-day period following the open-label injection.

In order to facilitate the planning of a Phase 3 pivotal study based on results of the primary and secondary efficacy parameters at 90-day and 180-day, the randomized treatment for the Main Phase will be unblinded and a snapshot of the database will be taken after all randomized subjects completed the 180-day assessment. Formal database preparation process will be performed to ensure the integrity and quality of the database and an interim analysis of the primary and secondary efficacy endpoints as well as the exploratory efficacy endpoints up to the 180-day time point will be performed. At the end of the study, the database will be locked. The database lock process will be performed to ensure the integrity and quality of the database; and formal analyses will be performed.

#### 1 STUDY OBJECTIVES

This Phase 2B IND Trial will be conducted to determine the safety and effectiveness of micronized dehydrated Human Amnion/Chorion Membrane (dHACM) as compared to the 0.9% sodium chloride, USP placebo control for the treatment of osteoarthritis of the knee.

#### 2 PRIMARY OBJECTIVES

The primary objective of this study is to determine the effectiveness of pain reduction and improvement of function after being treated with micronized dHACM as compared to the 0.9% sodium chloride, USP placebo control in patients with osteoarthritis of the knee.

#### 2.1 Primary Efficacy Endpoints

The co-primary efficacy endpoints are as follows:

Change in Visual Analog Scale (VAS) score for pain between baseline and 90 days

Page 4 of 27

• Change in Western Ontario and McMaster Universities (WOMAC) Osteoarthritis Index total score (Total WOMAC score), between baseline and 90 days

#### 2.1.1 VAS for Pain

The VAS for pain is a unidimensional measure of pain intensity, which has been widely used in diverse adult populations, including those with rheumatic diseases. The VAS for pain is a continuous scale comprised of a horizontal visual analog scale, usually 10 centimeters (100 mm) in length, and is most commonly anchored by "no pain" (score of 0) and "pain as bad as it could be" or "worst imaginable pain" (score of 100 [100-mm scale]).

## 2.1.2 Western Ontario and McMaster Universities (WOMAC) Osteoarthritis Index

The Western Ontario and McMaster Universities (WOMAC) osteoarthritis index is a validated, self-administered instrument developed in 1982 to evaluate a patient's disability as it relates to arthritis in the knee. The WOMAC index evaluates the level of disability due to osteoarthritis using 24 questions that comprise three subscales: pain, stiffness, and function. The Total WOMAC score is calculated as the sum of each item which is on a 0 to 4 point scale. The items total to a maximum of 96 points with a higher score indicating greater disability.

Should a patient fail to complete all items within a single questionnaire, missing data will be handled utilizing recommendations provided within the WOMAC User Guide, which states:

"If  $\geq$  two pain, both stiffness, or  $\geq$  four physical function items are omitted, the patient's response is regarded as invalid and the deficient subscale(s) should not be used in the analysis. Where one pain, one stiffness, or 1-3 physical function items are missing, we suggest substituting the average value for the subscale in lieu of the missing item value(s)."

#### 2.2 Primary Safety Endpoint

The primary safety endpoint is the proportion of product-related Adverse Events (AEs), Serious Adverse Events (SAEs), and unanticipated adverse events throughout the study.

#### 3 SECONDARY OBJECTIVES

The secondary objectives of this study are to determine the longer-term effectiveness of pain reduction and level of disability after being treated with micronized dHACM as compared to the 0.9% sodium chloride, USP placebo control in patients with osteoarthritis of the knee.

#### 3.1 Secondary Efficacy Endpoints

The secondary efficacy endpoints are as follows:

- Change in VAS score for pain between baseline and 180 days
- Change in Total WOMAC score between baseline and 180 days

#### 4 EXPLORATORY OBJECTIVES

[figure not shown]
The exploratory objectives of this study are intended to assess further the effectiveness in pain reduction and level of disability after being treated with micronized dHACM as compared to the 0.9% sodium chloride, USP placebo control in patients with osteoarthritis of the knee, throughout the course of the study.

As outlined in AIOA001 protocol, all study subjects will become eligible to receive an open-label injection of micronized dHACM at either of the 180-day, 270-day, or 365-day time points. Due to this change in treatment from the original protocol, all endpoints following the 180-day time point become exploratory objectives.

[figure not shown]

Page 6 of 27

[figure not shown]
#### 5 STUDY SUCCESS CRITERIA

#### **6 STUDY DESIGN AND PLAN**

Page 8 of 27

Page 9 of 27

Page 10 of 27

#### 7 STATISTICAL METHODS

#### 7.1 Statistical and Analytical Plans

#### 7.1.1 General Considerations

For the purposes of this protocol, osteoarthritis of the knee outcomes will be examined. The hypothesis to be tested is to confirm that the use of micronized dHACM offers a

Page 11 of 27

[figure not shown]
statistically significant advantage over 0.9% normal saline solution placebo for the treatment of osteoarthritis of the knee.

All statistical tests will be two-sided and will be performed at the significance, unless otherwise stated. Note that a penalty will be applied due to performing 2 planned interim analyses (see Section 7.1.11 for more details). Continuous data will be summarized by randomized Active and Control groups using descriptive statistics (number, mean, median, standard deviation [SD], minimum, and maximum). Categorical data will be summarized by randomized Active and Control groups using frequency tables (frequencies and percentages).

In addition to the efficacy analyses at the time point specified in the primary, secondary, and exploratory efficacy analyses, all efficacy parameters collected at various time points during the study will also be presented.

All analyses and summaries will be generated using SAS (SAS Institute, Inc., Cary, North Carolina).

#### 7.1.2 Analysis Set

Page 12 of 27

#### 7.1.3 Co-Primary Efficacy Analysis

This study consists of co-primary efficacy endpoints, which requires both endpoints to demonstrate success at 2-sided, level of significance.

#### 7.1.3.1 VAS Score for Pain Analysis (90 Days)

[figure not shown]
ANOVA on the change in VAS score for pain between baseline and 90 days with treatment as a fixed effect and study site as the block effect will be used to compare the efficacy between Active and Control groups at 2-sided, level of significance.

In the case of data not being normally distributed, nonparametric tests, such as Wilcoxon Rank Sum test, will be utilized to assess the treatment efficacy.

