
Name of Investigational Product: Allogeneic Micronized Dehydrated Human Amnion/Chorion Membrane (Micronized dHACM), a.k.a. AmnioFix Injectable
 
Study Design: A Phase 2B, Prospective, Double-Blinded, Randomized Controlled Trial of the Micronized dHACM Injection as Compared to Saline Placebo Injection in the Treatment of Osteoarthritis of the Knee
 
Indication: Knee osteoarthritis (OA)
 
Objective: To determine the safety and effectiveness of micronized dHACM as compared to the 0.9% Sodium Chloride Injection, USP placebo control for the treatment of knee osteoarthritis
 
Sample Size: Approximately 466 subjects will be enrolled in this study. Subjects to be randomized 1:1 in treatment arms.
 
Study Plan: The estimated enrollment period is 26 months. Each subject will receive 1 injection and be evaluated for efficacy and safety during a 12-month observation period. A second injection (open-label access to micronized dHACM) will be offered to all subjects at the 180-day, 270-day, and 365-day time points, see open-label access section below; it may only be used once. The study is expected to be completed within 44 months, inclusive of enrollment and follow-up for all subjects.
 
Procedures and Assessments:
 
 • Treatment (approx. 1 day): Screening, pre-procedure evaluation, injection procedure, baseline evaluation. • Clinical Follow-up (365-545 days): Routine follow-up with physical examination; pain, function, and quality of life measurements: Visual Analog Scale (VAS) for Pain, VAS for Satisfaction, Western Ontario and McMaster Universities (WOMAC) osteoarthritis index, and Knee injury and Osteoarthritis Outcome Score (KOOS) will be evaluated at baseline, 30 days, 60 days, 90 days, 180 days, 270 days and 365 days after the initial treatment, and at time of open-label access and 30 days, 60 days, 90 days, and 180 days following the second injection should the subject elect to receive the open-label access treatment. Subject pain diaries will be completed at predefined intervals. • Safety Follow-up (365-545 days): Adverse Events (AEs), Serious Adverse Events (SAEs), and Unanticipated Adverse Events will be evaluated at 30 days, 60 days, 90 days, 180 days, 270 days and 365 days after the initial treatment, and at time of open-label access and 30 days, 60 days, 90 days, and 180 days following the second injection should the subject elect to receive the open-label access treatment. 
Primary Efficacy Endpoints (VAS for Pain and Total WOMAC): The co-primary efficacy endpoints are:
 
 • The change in VAS score for pain between baseline and Day 90 • The change in WOMAC osteoarthritis index total score (Total WOMAC score) between baseline and Day 90 
Primary Safety Endpoint: The primary safety endpoint is the proportion of product-related Adverse Events (AEs), Serious Adverse Events (SAEs), and unanticipated adverse events throughout the study.
 
Secondary Endpoints: The secondary efficacy endpoints for this study are:
 
 • Change in VAS score for pain between baseline and 180 days • Change in Total WOMAC score between baseline and 180 days

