
Exploratory Endpoint:

For the cohort of subjects in the main phase of the study, i.e. who did not receive or have not yet received an open-label injection, the following exploratory endpoints will be assessed:

- Change in VAS score for pain between baseline and i-day (with i=30, 60, 270, and 365 days)
- Change in Total WOMAC score between baseline and i-day (with i=30, 60, 270, and 365 days)
- Change in pain, stiffness, and physical function WOMAC subscale scores between baseline and i-day (with i=30, 60, 90, 180, 270, and 365 days)
- Change in VAS score for satisfaction between baseline and i-day (with i=30, 60, 90, 180, 270, and 365 days)
- Change in KOOS scores between baseline and i-day (with i=30, 60, 90, 180, 270, and 365 days)
- Patient pain diary endpoints will be collected and summarized across applicable time points

For the cohort of subjects in the extension phase, i.e. who received the open-label injection and are within the period after the open-label injection, the following endpoints will be collected and summarized across applicable time points: VAS score for pain, Total WOMAC, WOMAC subscales for pain, stiffness and physical function, VAS score for satisfaction, KOOS, and pain diary entries.

Inclusion Criteria

All subjects enrolled must meet all the following criteria:

1. Age \geq 21 and \leq 80 years
2. Subject has a diagnosis of osteoarthritis (OA) defined as Grade 1 to 3 on the Kellgren Lawrence grading scale
3. Subject is willing and able provide informed consent and participate in all procedures and follow-up evaluations necessary to complete the study
4. Subject must have a VAS pain scale greater than 45

Exclusion Criteria

Any potential subjects meeting any of the following criteria will be excluded from enrollment and subsequent randomization.

1. Subject has a diagnosis of osteoarthritis (OA) defined as Grade 4 on the Kellgren Lawrence grading scale
2. BMI greater than 40 kg/m²
3. Subject has active infection at the injection site
4. Symptomatic OA of the contralateral knee or of either hip that is not responsive to acetaminophen (Tylenol®) and requires other therapy.
5. Subject has rheumatoid arthritis, psoriatic arthritis, or have been diagnosed with any other disorders that is the primary source of their knee pain, including but not limited to: osteonecrosis, radiculopathy, bursitis, tendinitis, tumor, cancer
6. Subject has documented history of gout or pseudo-gout

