7. Subject has autoimmune disease or a known history of having Acquired Immunodeficiency Syndromes (AIDS) or HIV
8. Subject has received any of the following to the target knee:
 - a. Intra-articular hyaluronic acid (HA) injection within 12 weeks prior to screening
 - b. Steroid or platelet rich plasma (PRP) injection within 12 weeks prior to screening
 - c. Has had or is planning to have major surgery or arthroscopy in the target knee within 26 weeks of treatment
 - d. History of a total knee arthroplasty
9. Subject has used an investigational drug, device or biologic within 12 weeks prior to treatment
10. Subject has a history of immunosuppressive or chemotherapy in the last 5 years
11. Subject has had prior radiation at the site
12. Subject is currently taking anticoagulant therapy (excluding Plavix or Aspirin)
13. Subject is pregnant or plans to become pregnant within 365 days of treatment
14. Subject has any significant medical condition that, in the opinion of the Investigator, would interfere with protocol evaluation and participation
15. Subject is a worker's compensation patient
16. Subject is a prisoner

Open-Label Access:

All study subjects will be eligible to receive one injection of micronized dHACM at either of the Day 180, Day 270, and Day 365 time points. The investigators and subjects will remain blind to the initial treatment assignment at this time, and until the study is unblinded.

Subjects who receive the open-label access treatment will continue to be followed for 180 days after this second injection, regardless of the time at which treatment was received.

Statistical Methods:

The change in VAS score for pain and Total WOMAC score between baseline and Day 90 (primary endpoints) and between baseline and Day 180 (secondary endpoints) will be compared between the treatment arms using an ANOVA with treatment as a fixed effect and study site as the block effect.

For the purposes of this protocol, we will be examining knee osteoarthritis. The hypothesis to be tested is to confirm that the use of micronized dHACM offers a statistically significant advantage over placebo control.

Efficacy and safety data will be submitted for evaluation following the completion of the study follow-up.

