### 7.1.3.2 Total WOMAC Score Analysis (90 Days)

Page 13 of 27

Page 14 of 27

[figure not shown]
ANOVA on the change in Total WOMAC score between baseline and 180 days with treatment as a fixed effect and study site as the block effect will be used to compare the efficacy between Active and Control groups at 2-sided, level of significance.

In the case of data not being normally distributed, nonparametric tests, such as Wilcoxon Rank Sum test, will be utilized to assess the treatment efficacy.

[figure not shown]

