#### 7.1.6 Adjustments for Covariates

Not applicable.

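### Free improvement: the Day-90 and Day-180 analyses leave the collected baseline score out of the model; adding it as a covariate cannot reduce large-sample precision and usually raises it

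*SAP*

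**What the plan says.** - **Protocol, Statistical Methods.** One model covers all four endpoints, that is, change in VAS pain and in Total WOMAC at Day 90 (primary) and Day 180 (secondary). The arms are compared "using an ANOVA with treatment as a fixed effect and study site as the block effect".
- **SAP 7.1.3.1 (VAS, Day 90).** The analysis is "ANOVA on the change in VAS score for pain between baseline and 90 days with treatment as a fixed effect", with site as the block term.
- **SAP, readable text after heading 7.1.3.2.** The Day-180 WOMAC analysis has the same form: "ANOVA on the change in Total WOMAC score between baseline and 180 days with treatment as a fixed effect", again with site. The SAP text for WOMAC at Day 90 and VAS at Day 180 is not readable, so for those two endpoints the model is taken from the protocol.
- **SAP 7.1.6 (Adjustments for Covariates).** The whole entry is "Not applicable". This is visible text, so leaving out baseline is a stated choice and not an effect of redaction.
- **Fallback for non-normal data (SAP 7.1.3.1, repeated in the WOMAC text).** "nonparametric tests, such as Wilcoxon Rank Sum test, will be utilized to assess the treatment efficacy". No stratification by site is stated.
- **Data available (protocol synopsis, Procedures and Assessments).** The pain and function scores "will be evaluated at baseline, 30 days, 60 days, 90 days, 180 days" and later.
- **Success rule (SAP 7.1.3).** The co-primary design "requires both endpoints to demonstrate success".

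**The concern.** Analysing change without a baseline term fixes the coefficient of baseline at 1. ANCOVA estimates that coefficient from the data. When the true slope of follow-up on baseline is not 1, the change score carries baseline noise that the model could have removed, and the standard error of the treatment difference is larger than it need be.

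This is a loss of efficiency and not an error. Under randomization the planned ANOVA is unbiased and its type I error is sound.

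What is at stake is power. Success needs both co-primary endpoints, so imprecision on either one lowers the chance of joint success. The SAP introduction also says that the Day-90 and Day-180 results will be used to plan Phase 3, and more precise estimates help there too. If the data are judged non-normal, the rank-sum test as named also loses the planned site adjustment.

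**Working it through.** **Inputs from the documents.** About 466 subjects, randomized 1:1; two-sided tests; baseline VAS and WOMAC collected; entry rule "Subject must have a VAS pain scale greater than 45". The public text shows no significance level, power, effect size, SD or baseline-to-follow-up correlation. The 466 therefore cannot be reproduced, and every size below rests on assumptions.

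**1. Direction.** Let s0 and s1 be the within-arm SDs at baseline and follow-up, and r their correlation.

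- Variance of change: s0² + s1² − 2·r·s0·s1
- Residual variance under ANCOVA: s1²(1 − r²)
- Difference: (s0 − r·s1)², which is never negative and is zero only when the slope r·s1/s0 equals 1

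So in large samples with 1:1 allocation, adding baseline cannot reduce precision. The finite-sample cost is one degree of freedom out of more than 400.

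**2. Size without truncation.** Proportional reduction = (s0 − r·s1)² / (s0² + s1² − 2·r·s0·s1).

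| s0/s1 | r = 0.2 | r = 0.3 | r = 0.5 | r = 0.7 |
|---|---|---|---|---|
| 1.0 | 40% | 35% | 25% | 15% |
| 0.8 | 27% | 22% | 11% | 2% |
| 0.6 | 14% | 9% | 1% | 2% (0% at r = 0.6) |

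With equal SDs the reduction is (1 − r)/2. The same precision would then come from 466 × 0.65 = 303 subjects at r = 0.3, or 466 × 0.85 = 396 at r = 0.7.

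**3. Effect of the VAS entry rule.** Start from unit SDs with slope b, so the residual variance is 1 − b². Cut the baseline SD to k and hold the slope. The reduction is (1 − b)²k² / [1 − b² + (1 − b)²k²].

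- k = 0.8: 26% at b = 0.3, 10% at b = 0.7
- k = 0.6: 16% at b = 0.3, 6% at b = 0.7

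Truncation makes the VAS gain smaller. No entry limit is set on Total WOMAC.

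**4. Joint power.** Assume 80% power for each endpoint under ANOVA, two-sided 0.05, and correlation 0.5 to 0.9 between the test statistics (bivariate normal). A variance reduction g multiplies the expected z of 1.960 + 0.842 = 2.802 by 1/√(1 − g).

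| Variance reduction | Joint power |
|---|---|
| None (ANOVA) | 69–75% |
| 2% on both | 70–76% |
| VAS 0%, WOMAC 15% | 73–78% |
| VAS 10%, WOMAC 25% | 78–82% |

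**5. Simulated VAS example.** Assumptions: 466 subjects, 20 sites (site SD 5), baseline normal(65, 18) kept if above 45 and at most 100 (resulting SD 13.2), residual SD 20, true difference 6, 3,000 runs per setting.

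| Power at slope | 0.3 | 0.5 | 0.7 |
|---|---|---|---|
| ANOVA on change | 83% | 86% | 88% |
| ANCOVA | 88% | 90% | 89% |
| Wilcoxon rank-sum | 80% | 84% | 86% |
| Rank ANCOVA (baseline and site) | 86% | 88% | 87% |

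Null rejection was 5.1 to 5.8% for all four tests.

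Closed-form check of the first two rows: the variance of change is 400 + (1 − b)² × 13.2², or 485, 444 and 416 at the three slopes, against 400 for ANCOVA. The reductions are 18%, 10% and 4%. With standard error √(4 × variance/466), power is 84%, 87% and 89% for ANOVA and 90% for ANCOVA at every slope. The spread in the simulated ANCOVA row is therefore simulation noise.

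**The case against.** The strongest reply is that nothing here is wrong. The planned ANOVA is valid, and the protocol and the readable SAP text agree on it. The benefit cannot be sized from the documents: it runs from 0 to 40% on the assumptions above, and the larger figures need equal SDs, a poor default for VAS given the entry rule. At slope 0.7 the simulated VAS gain is about one power point, and 2% on both endpoints adds about one point to joint power. All of this stands, and it limits the claim to a free improvement of uncertain size.

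Three further points stand in part.

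- **Fallback.** The SAP offers the rank-sum test only as an example, so a site-stratified test is not excluded; none is specified, however. The guarantee in step 1 is for ANCOVA against ANOVA. For rank ANCOVA against Wilcoxon, the support is simulation under assumed values.
- **Timing.** SAP 7.1.12 places an interim analysis at 50% of the study population, and the public text of 7.1.11 is blank. If that look is unblinded and has already taken place, changing the primary model is no longer free.
- **Redaction.** Other SAP sections are largely blank, so a supportive baseline-adjusted analysis cannot be ruled out, although the entry in 7.1.6 makes it unlikely.

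None of these removes the case for making the change in time.

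**Conclusion.** The concern holds, as an efficiency improvement and not as a validity fault. The direction is certain in large samples under 1:1 allocation: baseline-adjusted ANCOVA is at least as precise as the planned ANOVA for all four endpoints, and strictly more precise unless the slope of follow-up on baseline is 1. The size is assumed. Plausible variance reductions run from about 0 to 40%, probably smaller for VAS than for Total WOMAC. In the joint-power examples, a starting 69–75% becomes 70–76% at the low end and 78–82% with reductions of 10% for VAS and 25% for WOMAC. Those figures assume 80% power per endpoint and a two-sided 0.05 level, neither of which is visible in the documents. The change is worth making because it needs no new data, provided it comes before any unblinded look.

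**What to change.** 1. Prespecify ANCOVA for all four endpoints: change = treatment + study site + the corresponding baseline score (VAS pain for VAS pain, Total WOMAC for Total WOMAC).
2. Replace the entry in SAP 7.1.6 with these covariates, and revise the SAP endpoint sections and the protocol's Statistical Methods to match.
3. Keep the unadjusted ANOVA on change as a sensitivity analysis.
4. Replace the open-ended nonparametric fallback with a named rank-based test that adjusts for baseline and site, for example rank ANCOVA.
5. Finalize the change before any unblinded look. That means before the 50% interim in SAP 7.1.12 if that look is unblinded; only if it is not can the change wait until the Day-180 unblinding described in the SAP introduction.

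The cost is wording in two documents and one degree of freedom per model. A switch after an unblinded look would appear data-driven and would no longer be free.
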